5.6.6 Safety Analyses

5.6.6.1 Adverse Events

Procedure safety will be assessed by recording all AEs that occur on the day of the treatment procedure. Longer-term safety will be assessed by recording at each follow-up visit any untoward medical occurrence since baseline. Each AE will be assessed for severity and relationship to study device and/or procedure. In addition to evaluating procedural and longer-term safety, subjects who become pregnant after the procedure will be asked to report any pregnancy complications.

AEs will be classified by onset date into the following time periods:

- Day 0 (procedure day)
- Days 1-6 post-op (1st week)
- Days 7-30 post-op (1st month)
- Days 0-30 (aggregate of all AEs during 1st month)
- Days 31-90
- Days 91-180
- Days > 180

Descriptions of AEs will include the date of onset, the date the AE resolved, stabilized, or returned to baseline, the severity of the AE, and the outcome. All reported AEs will be summarized by the number of subjects reporting AEs, severity, seriousness, and relationship to the VizAblate device and/or procedure. Summaries will also be presented for device-related AEs, procedure-related AEs, and AEs by anesthesia type administered to the subject.

AEs will be summarized both by subject incidence rate and event incidence rate. In addition, AEs will be summarized by severity and relationship to the VizAblate procedure and/or device, such that each subject will be counted only once for each AE by using the AE with the highest severity/greatest relationship within each category.

All information pertaining to AEs noted during the study will be listed by subject, detailing verbatim given by the Investigator, start date, stop date, severity, and VizAblate procedure-relatedness. The AE onset will also be shown relative (in number of days) to the day of the VizAblate procedure. The sponsor is responsible for classifications of adverse events; in case of disagreements between the sponsor and the investigator in which the investigator's opinion is that the event is more serious and/or more related, both opinions will be included in adverse event reports.

Serious adverse events (SAEs) will be tabulated by subject. In addition, a list of subjects who discontinued from the study and a list of subjects who experienced SAEs will also be provided.

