12.3 Follow-up Phase

- A. Follow-up visits will occur in accordance with Table 6 below. The day of the Sonata treatment represents Day 0. Study visits that do not occur within the below time windows will be considered protocol deviations.

Table 6 Follow-up (FU) Visit Windows

Visit	Allowed Visit Date Range
FU Visit 1 - 10 days	± 4 days
FU Visit 2 - 30 days	± 1 week
FU Visit 3 - 3 months	± 2 weeks
FU Visit 4 - 6 months	± 4 weeks
FU Visit 5 - 12 months	± 2 months
FU Visit 6 - 2 years	± 2 months
FU Visit 7 - 3 years	± 2 months

- B. The measurements and evaluations that will occur at each follow-up visit are provided below.

- 1) Follow-up Visit 1: 10 Days (± 4 days)
(Phone Call or visit at Investigator's discretion)

(a) Adverse Events

The primary purpose of Follow-up Visit #1 is to assess safety. Subjects will be asked if they have experienced any untoward medical occurrences since the Sonata treatment. If so, these events will be recorded on the Adverse Event case report form, in accordance with the procedures outlined later in this protocol.

(b) Post-treatment follow up

Subjects will be asked whether there is any change to their medical status. Subjects will be asked specifically if they have experienced any signs or symptoms of fibroid shedding: cramping, bleeding, passage of any tissue per vaginam.

(c) Concomitant Medications

Subjects will be asked about concomitant medications, noting in particular concomitant medications taken for the treatment of HMB.

(d) Adherence with/Continuance of Birth Control Method

Subjects will be asked if they are adhering to their chosen method of birth control, and if there have been any changes in their birth control method, including changes to medication type and preparation.

2) Follow-up Visit #2: 30 Days (\pm 1 week)

(a) Adverse Events

Subjects will be asked if they have experienced any untoward medical occurrences since the Sonata treatment. If so, these events will be recorded on the Adverse Event case report form, in accordance with the procedures outlined later in this protocol.

(b) Return to Normal Daily Activity

Subjects will be asked to submit their completed Treatment Recovery Questionnaire (Appendix C). Subjects who are not back to normal activity will be followed up by phone visits weekly until the subject has resumed normal activity or the reason for not resuming normal activity is not expected to change.

(c) Surgical Reintervention

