- A supply of sanitary products in sufficient quantity to cover use for one menstrual cycle for the completion of the PBAC.

- 4) Follow-up Visits #4-5: 6 Months (\pm 4 weeks) and 12 Months (\pm 2 Months)
- (a) MRI (12 months only)
 - (b) UFS-QOL, EQ-5D, and WPAI:SHP Questionnaires
Subjects will be asked to return their completed EQ-5D questionnaire and will be asked to complete the UFS-QOL and WPAI:SHP questionnaires.
 - (c) Menstrual Diary
Subjects will be asked to return their completed menstrual diary (PBAC) for the menstrual cycle preceding the visit.
 - (d) Adverse Events
Subjects will be asked if they have experienced any untoward medical occurrences since the Sonata treatment. If so, these events will be recorded on the Adverse Event case report form, in accordance with the procedures outlined later in this protocol.
 - (e) Surgical Reintervention
Subjects will be asked if they have undergone any surgical procedure to treat their heavy menstrual bleeding. If so, the procedure performed and the date of the reintervention will be recorded.
 - (f) Pregnancy/Pregnancy Outcomes
Subjects will be asked if they have become pregnant since the last follow-up visit. If so, the subject will be released from all protocol specified follow-up assessments and visits, however the subject will be followed and pregnancy outcomes (including any complications) will be recorded as described in Section 10.6 of this protocol.
 - (g) Post-treatment follow-up
Subjects will be asked whether there is any change to their medical status. Subjects will be asked specifically if they have experienced any signs of fibroid shedding: cramping, bleeding, passage of any tissue per vaginam.
 - (h) Amenorrhea
If the subject becomes amenorrheic, a pregnancy test (urine or serum hCG) will be performed and, if negative, a serum FSH level determination will also be obtained.
 - (i) Concomitant Medications
Subjects will also be asked about concomitant medications, noting concomitant medications taken for the treatment of excessive uterine bleeding.

(j) Subject Satisfaction

Subjects will be asked to rate their satisfaction with the treatment, with responses based on a 6-point Likert scale ranging from “very satisfied” to “very dissatisfied”. They will also be asked if they would recommend the treatment to a friend with the same health problems using a 4-point scale from “definitely yes” to “definitely not”.

(k) Overall Treatment Effect (OTE)

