Subjects will be asked to indicate whether their uterine fibroid symptoms have improved, remained the same, or worsened. If the subject indicates that her symptoms have improved, she will be asked to rate the degree of improvement on a 7-point scale from “almost the same, hardly better at all” (1) to “a very great deal better” (7). If the subject indicates that her symptoms worsened, she will be asked to rate the degree of worsening on a 7-point scale from “almost the same, hardly worse at all” (-1) to “A very great deal worse” (-7).

(l) Adherence with/Continuance of Birth Control Method

Subjects will be asked if they are adhering to their chosen method of birth control, and if there have been any changes in their birth control method, including changes to medication type and preparation.

Note: During follow-up visit #4, the subject will be given study materials in anticipation of follow-up visit #5, which will be comprised of the following:

- A copy of the EQ-5D Questionnaire (Appendix A). The EQ-5D should be completed during the subject’s 12th menstrual cycle post-treatment, preferably on the first full day of bleeding. It should be completed based solely on symptoms from that cycle. If the subject has become amenorrheic, the EQ-5D may be completed at any time during the follow-up visit window.
- Menstrual diary (PBAC) with completion instructions noting that only the sanitary products provided should be used during the study while completing the PBAC.
- A supply of sanitary products in sufficient quantity to cover use for one menstrual cycle for the completion of the PBAC.

- 5) Follow-up Visit 6 and 7: 2 and 3 years
(Phone Call or mail at Investigator's discretion)
- (a) UFS-QOL, EQ-5D, and WPAI:SHP Questionnaires
Subjects will be asked to return their completed EQ-5D questionnaire and will be asked to complete the UFS-QOL and WPAI:SHP questionnaires.
- (b) Pregnancy/Pregnancy Outcomes
Subjects will be asked if they have become pregnant since the last follow-up visit. If so, the subject will be released from any remaining protocol specified follow-up assessments and visits, however the subject will be followed and pregnancy outcomes (including any complications) will be recorded as described in Section 10.6 of this protocol.
- (c) Adverse Events

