Subjects will be asked if they have experienced any untoward medical occurrences related to the abdomen and/or pelvis since the Sonata treatment. If so, these events will be recorded on the Adverse Event case report form, in accordance with the procedures outlined later in this protocol.
- (d) Surgical Reintervention
Subjects will be asked if they have undergone any surgical procedure to treat their heavy menstrual bleeding. If so, the procedure performed and the date of the reintervention will be recorded.
- (e) Subject Satisfaction
Subjects will be asked to rate their satisfaction with the treatment, with responses based on a 6-point Likert scale ranging from "very satisfied" to "very dissatisfied". They will also be asked if they would recommend the treatment to a friend with the same health problems using a 4-point scale from "definitely yes" to "definitely not".
- (f) Overall Treatment Effect (OTE)
Subjects will be asked to indicate whether their uterine fibroid symptoms have improved, remained the same, or worsened. If the subject indicates that her symptoms have improved, she will be asked to rate the degree of improvement on a 7-point scale from "almost the same, hardly better at all" (1) to "a very great deal better" (7). If the subject indicates that her symptoms worsened, she will be asked to rate the degree of worsening on a 7-point scale from "almost the same, hardly worse at all" (-1) to "A very great deal worse" (-7).

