14.2 Principal Investigator responsibility - Safety reporting

- A. Carefully monitor all subjects during the study (subsequent to consent) for possible adverse events, and fully investigate any observed AE. All AEs will be followed, with laboratory tests if appropriate, until resolution or until the Investigator judges the outcome to be chronic or stable,
- B. Record every adverse event and observed device deficiency, together with an assessment, using the appropriate case report form. The case report form for adverse events will include an assessment of severity, seriousness, relatedness to the investigational device and/or procedure, and whether it was anticipated in the investigational plan,
- C. Report to Gynesonics, within 24 hours of learning of an event, all serious adverse events and any device deficiencies that could have led to a serious adverse device effect; this information shall be promptly followed by detailed written reports using the specific medical diagnosis, or using signs, symptoms or abnormal laboratory values if no medical diagnosis can be identified. The PI shall supply Gynesonics upon request with any additional information related to the safety reporting of a particular event,

A follow-up written report of all serious adverse events (SA(D)Es) shall be *emailed or faxed* to Gynesonics within 48 hours and shall include the following information:

- 1) Nature of adverse event
 - 2) Severity of adverse event
 - 3) Date of onset of adverse event
 - 4) Date of resolution of adverse event, if applicable
 - 5) Statement as to why it is considered unanticipated, if applicable
 - 6) Statement as to why it is considered serious, if applicable
 - 7) Statement as to the degree to which it is considered device related, and why
 - 8) Results of any diagnostic tests that were performed
 - 9) Description of any treatment administered
 - 10) Statement of subject's current clinical status
 - 11) Investigator's signature and date
- D. Report to the IRB / EC all serious adverse events and any device deficiencies that could have led to a serious adverse device effect as soon as possible, but in no event later than 10 working days after the investigator first learns of the occurrence.

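### The adverse event question narrows to the abdomen and pelvis at years 2 and 3, but the SAP describes unrestricted recording at every visit and pools all onsets after Day 180, so late all-cause rates would tend to be understated if 3-year data are included

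*SAP*

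**What the plan says.** **Recording rule.** SAP 5.6.6.1 states: "Longer-term safety will be assessed by recording at each follow-up visit any untoward medical occurrence since baseline". The same sentence stands in the safety row of Protocol Table 2, where the endpoint is named as adverse device effects and, like the other secondary endpoints, is reached at 12 months.

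**What women are asked.** Protocol 12.3 B gives the question visit by visit. At 10 days, 30 days, 3 months, 6 months and 12 months it is: "Subjects will be asked if they have experienced any untoward medical occurrences since the Sonata treatment". Under "Follow-up Visit 6 and 7: 2 and 3 years", contacts made by phone or mail, it becomes: "Subjects will be asked if they have experienced any untoward medical occurrences related to the abdomen and/or pelvis since the Sonata treatment".

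**What investigators must record.** Protocol 14.2 B: "Record every adverse event and observed device deficiency, together with an assessment, using the appropriate case report form". It sets no limit by body region or year.

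**Schedules.** Protocol Table 4 and SAP Table 2 mark adverse events at years 2 and 3 with no footnote on scope.

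**How events are tabulated.** SAP 5.6.6.1 classifies events by onset. The last period is open-ended and starts after Day 180. "AEs will be summarized both by subject incidence rate and event incidence rate", with no denominator defined. SAP 5.4 bases the final report on the final locked database, and SAP 5.6.8.3 plans no interim analysis. The SAP does not mention the narrower question at years 2 and 3.

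**The concern.** The scope of the question changes at the 12-month visit, and the SAP's time periods do not follow that change. One row would hold events from months 6 to 12, when women were asked about anything, and events from years 2 and 3, when they were asked only about one body region. Someone reading that row beside the SAP sentence would take it as complete capture to 3 years. A low all-cause or serious event rate could then reflect the question rather than the women's experience.

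Seven planned tables are broken down by time period: 14.3.1.2.1 to 14.3.1.2.5, and 14.3.1.6.1 and 14.3.1.6.2 for serious events. The device-related and procedure-related tables (14.3.1.3.x and 14.3.1.4.x) carry no time period in their titles, so they would pool all follow-up.

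A smaller matter goes with this. The safety endpoint is reached at 12 months, but no listed onset period ends there, so no planned table shows it directly.

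**Working it through.** The plan states no late adverse event rate, so there is no figure to reproduce. The check compares the passages and then measures how much of the last period falls under each question.

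**1. Passages side by side**

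| Contact | Question (Protocol 12.3 B) | SAP 5.6.6.1 and Protocol Table 2 |
|---|---|---|
| 10 days to 12 months | any occurrence | any occurrence: agrees |
| 2 and 3 years | abdomen and/or pelvis only | any occurrence: disagrees |

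In both schedules, concomitant medications and the medical-history update also stop at 12 months. Two routes by which an unprompted non-pelvic event might surface are therefore absent at years 2 and 3.

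**2. Calendar time in the last period**

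Inputs: the period starts after Day 180 (SAP 5.6.6.1). "FU Visit 5 - 12 months" is taken as Day 365 and 3 years as Day 1095 (Protocol Table 6), each with a window of 2 months either way, taken as 61 days.

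- Whole period: 1095 − 180 = 915 days
- Unrestricted question: 365 − 180 = 185 days, and 185/915 = 20.2%
- Restricted question: 1095 − 365 = 730 days, and 730/915 = 79.8%

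At the extremes of the windows:

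- 12-month visit on Day 304, 3-year contact on Day 1156: 852/976 = 87.3% restricted
- 12-month visit on Day 426, 3-year contact on Day 1034: 608/854 = 71.2% restricted

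**3. What this could do to an all-cause rate**

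Let q be the share of late events that are abdominal or pelvic. The documents do not give q; a range of 0.25 to 0.75 is assumed. Also assume a constant event rate, follow-up to 3 years, and no unsolicited reporting of other events after month 12. Then

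observed/true = (185 + q × 730) / 915

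| q (assumed) | Calculation | Ratio | Ratio across visit windows |
|---|---|---|---|
| 0.25 | 367.5/915 | 0.40 | 0.35 to 0.47 |
| 0.50 | 550/915 | 0.60 | 0.56 to 0.64 |
| 0.75 | 732.5/915 | 0.80 | 0.78 to 0.82 |

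For abdominal and pelvic events alone, q = 1 and the ratio is 1.00.

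Subject incidence moves the same way. With an assumed rate r per woman-year and q = 0.50, true incidence is 1 − exp(−r × 915/365) and observed incidence is 1 − exp(−r × 550/365). This gives 39% against 26% at r = 0.2, 71% against 53% at r = 0.5, and 92% against 78% at r = 1.0.

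These figures illustrate the mechanism and do not estimate the bias in this trial. Any unsolicited reporting would bring the ratios nearer to 1.

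**4. After a split at the 12-month visit**

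On nominal days, Days 181 to 365 (185 days) are wholly under the unrestricted question and Days 366 to 1095 (730 days) wholly under the restricted one. Neither row is mixed.

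**The case against.** The case on the other side is substantial, and much of it stands.

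- **Years 2 and 3 are postmarket.** Protocol 4 I says those timepoints are not needed for a marketing application. In a table run on 12-month data, the last row would hold only fully solicited events. That is right, but the SAP states no such cut for adverse events and points to the final locked database. The mixing is therefore conditional on 3-year data being included.
- **The endpoint is adverse device effects.** The abdomen and pelvis are the treated region, and most device effects are likely to arise there. They are still asked about, so bias in device-related rates should be smaller. This stands. All-cause and serious events are also tabulated, however, and they are exposed.
- **Protocol 14.2 still applies.** Section 12.3 governs what women are asked; 14.2 governs what investigators record once they know of an event, and it requires serious events to be reported within 24 hours of learning of them. Both can be followed, so a reader who infers a flat contradiction between them goes too far. The clear conflict is between the SAP and Table 2 sentence and 12.3 B 5 (c). A general duty to record does not make unsolicited capture equal to solicited capture.

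Three stronger readings are tempting, and the documents do not support them.

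- A reader might infer that about 80% of non-pelvic events in the last row would be missing. The 80% is a share of calendar time. It becomes a loss of events only under a constant rate, no unsolicited reporting, nominal visit days and full retention.
- A reader might infer that late cardiac or thromboembolic harm from the device would be hidden. Protocol 13.1 lists such events as risks of use, but the documents place them around the procedure: prophylaxis is tied to treatment, and the one reported death came several days after it. Nothing points to a device-related excess after month 12.
- A reader might infer that the 12-month safety endpoint cannot be obtained. SAP 5.6.6.1 lists each event with its onset day relative to the procedure, so a 12-month count can be derived. What is missing is a planned table that shows it.

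**Conclusion.** The point holds in a limited form. The SAP and Protocol Table 2 describe unrestricted recording at every follow-up visit, while Protocol 12.3 restricts the question at years 2 and 3. The open period after Day 180 has no break where the question changes. If 3-year data enter the tables, the all-cause and non-pelvic adverse event and serious adverse event rates in that row would tend to be understated.

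The expected direction follows from the design; the size cannot be stated. About 80% of the row's nominal calendar time (71% to 87% across the visit windows) is under the narrower question. Turning that into a bias needs the abdominopelvic share of late events and the extent of unsolicited reporting. Abdominal and pelvic rates are unaffected, and the co-primary endpoints are not involved. The change should be made because the late safety rows would otherwise be labelled as more complete than they are.

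**What to change.** 1. **Split the last onset period in SAP 5.6.6.1** into Day 181 to the 12-month visit, and after the 12-month visit, with the second labelled as abdominal/pelvic events solicited only. State which day closes the earlier period for a woman who missed the 12-month visit.
2. **Define the denominator of the later period** as women still in follow-up after the 12-month visit, and report beside it the numbers contacted at year 2 and at year 3. Using only women contacted would leave out women whose events reached the site by another route, and would leave unclear how to count those reached at one contact only.
3. **Add a cumulative row from Day 0 to the 12-month visit**, following the aggregate row the SAP already has for Days 0 to 30. Add it to the device-related and procedure-related tables as well.
4. **Reconcile the text.** Correct the recording sentence in SAP 5.6.6.1 and Protocol Table 2 so that it agrees with Protocol 12.3 B 5 (c), or otherwise bring those passages into agreement.

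The split, labels and cumulative row need no new data, only revised wording and a few more rows or columns in planned tables. The cost is that the 3-year safety statement becomes narrower: for the period after the 12-month visit it can claim solicited capture of abdominal and pelvic events only.

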5.6.7 Determination of Sample Size

SAS® PROC POWER was used to calculate the following sample sizes. The co-primary endpoint of Reduction in MBL at 12 months will be analyzed using 95% exact confidence intervals. In order to claim study success, the lower limit of the 95% confidence interval must exceed the pre-specified threshold (described in the table below).

Table 4: Determination of Sample Size

Co-Primary Endpoint	Lower Confidence Limit Success Criterion	Assumed Subject Success Rate	N to Achieve 90% Power
Reduction in MBL at 12 months	≥45%	60%	125
Rate of surgical reintervention for HMB due to treatment failure at 12 months	≥75%	90%	75

To account for an assumed 20% subject dropout rate (subjects lost to follow-up), a sample size of at least 125 and up to 150 treated subjects will be enrolled.

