Submucous fibroid	A fibroid that lies beneath and makes contact with the overlying endometrium to the extent that there is distortion of the endometrial cavity. These are subdivided into three categories: type 0, type 1, and type 2.
Subserous fibroid	A fibroid that makes contact with the uterine serosa (visceral peritoneum) to the extent that it distorts the external contour of the uterus. These are subdivided into three categories: type 5, type 6, and type 7.
Type 0 fibroid	An intracavitary pedunculated fibroid
Type 1 fibroid	A submucous fibroid that is < 50% intramural
Type 2 fibroid	A submucous fibroid that is ≥ 50% intramural
Type 3 fibroid	A fibroid that contacts the endometrium but is otherwise intramural
Type 4 fibroid	A fibroid that is entirely surrounded by myometrium
Type 5 fibroid	A subserous fibroid that is ≥ 50% intramural
Type 6 fibroid	A subserous fibroid that is < 50% intramural
Type 7 fibroid	A pedunculated subserous fibroid
Type 2-5 fibroid	A fibroid that is submucous and subserous, each with less than half their diameter in the endometrial and peritoneal cavities, respectively
TVUS	Transvaginal Ultrasound
UADE	Unanticipated Adverse Device Effect
UAE	Uterine Artery Embolization
UFS-QOL	Uterine Fibroid Symptom and Quality of Life Questionnaire
VAS	Visual Analog Scale
WPAI:SHP	Work Productivity and Activity Impairment Questionnaire: Specific Health Problem

4 **STUDY ABSTRACT**

A. STUDY TITLE

Evaluation of the Gynesonics System for Transcervical Treatment of Symptomatic Uterine Fibroids with Radiofrequency Ablation under Integrated Intrauterine Sonography Guidance

B. SHORT TITLE

Sonography-Guided Transcervical Ablation of Uterine Fibroids (SONATA)

C. PROTOCOL NUMBER

CL 04502

D. STUDY OBJECTIVE

To establish the safety and effectiveness of the Sonata System in the treatment of symptomatic uterine fibroids.

E. STUDY DESIGN

Prospective, longitudinal, multicenter, single-arm cohort study with the subject serving as her own control

F. STUDY DEVICE

Sonata® System

G. NUMBER OF SUBJECTS

147 treated subjects; at least 50% will be enrolled and treated within the United States

H. NUMBER OF SITES

Up to 27 investigational sites in the United States, Europe, and Mexico will participate in this study. At least half of the sites will be in the United States.

I. FOLLOW-UP

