8 STUDY DESIGN AND SAMPLE SIZE

The study is designed as a prospective, longitudinal, multicenter, single-arm cohort study with the subject serving as her own control. A baseline assessment of Menstrual Blood Loss (MBL), fibroid volume, fibroid-associated symptoms/quality-of-life (UFS-QOL), general quality of life (EQ-5D), and work productivity and activity impairment (WPAI:SHP) will be collected, which will allow a subject to serve as her own control.

The single-arm design is consistent with regulatory precedent for pivotal studies of devices intended for the treatment of uterine fibroids. Likewise, the co-primary endpoints of reduction in menstrual blood loss and reintervention are consistent with regulatory precedent for fibroid studies. Use of the pictorial blood loss assessment chart is consistent with regulatory precedent for other pivotal studies involving menstrual blood loss as a primary endpoint, such as studies of thermal endometrial ablation devices. The validity of the patient inclusion / exclusion criteria is supported by inclusion of patients with heavy menstrual bleeding (HMB) and fibroid types likely responsible for HMB, and exclusion of other causes such as adenomyosis or as indicated by presence of irregular bleeding.

The sample size for this study is at least 125 treated subjects to achieve 90% power with α level equal to 0.05 and an assumed success rate of 60%. To allow for 15% loss to follow-up, up to 147 women will be enrolled and treated. The statistical rationale for this sample size may be found in the Statistical Analysis Plan.

Overall study duration (first subject enrolled through last subject exit) will be comprised of approximately 22 months of subject enrollment and 36 months of follow-up post-treatment for a total study duration of up to 58 months.

Study duration for an individual subject, once she provides her informed consent, will be up to 3 months for screening (including baseline measurements) and treatment, and 36 months for follow-up for a total duration of approximately 38-39 months.

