19.1 Sample Size

A. Reduction in Menstrual Blood Loss (MBL) at 12 months

Ho: Population proportion of MBL success < 0.45

Ha: Population proportion of MBL success ≥ 0.45

In order to claim study success for MBL, the lower limit of the 95% confidence interval must be ≥ 0.45 .

Under the assumption that the MBL success rate is at least 0.60, a sample size of 125 subjects provides better than 90% power to demonstrate that the lower limit of the 95% confidence interval exceeds the pre-specified threshold.

B. Rate of surgical re-intervention for HMB

Ho: Population proportion of no surgical re-intervention success < 0.75

Ha: Population proportion of no surgical re-intervention success ≥ 0.75

In order to claim study success for surgical re-intervention, the lower limit of the 95% confidence interval must be ≥ 0.75 . Under the assumption that the no surgical re-intervention success rate is at least 0.9, a sample size of 75 provides better than 90% power to demonstrate that the lower limit of the 95% confidence interval exceeds the pre-specified threshold.

C. Allowance for expected dropout rate

To account for an assumed 15% subject dropout rate (subjects lost to follow-up at the 12-month visit), a sample size of 147 treated subjects will be enrolled and treated.

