5.6.8.2 Handling of Dropouts or Missing Data

Reduction in MBL at 12 Months

Missing 12-month menstrual blood loss data will be imputed using last observation carried forward (LOCF). Subjects which undergo surgical reintervention to manage fibroid symptoms prior to 12 months will be excluded from the Reduction in Menstrual Blood Loss analysis.

Surgical Reintervention for HMB due to Treatment Failure at 12 Months

Life-Table methods will be used to calculate the success rate and 95% confidence interval for the rate of surgical reintervention during 12 months. Therefore, subjects that are discontinued prior to 12 months for reasons other than surgical reintervention will be considered censored.

Sensitivity Analyses

Sensitivity analyses will also be conducted to examine the impact of missing data. A worst-case analysis (all missing data imputed as failures) and best-case analysis (all missing data imputed as successes) will be performed. In addition, a tipping point analysis will be performed.

Secondary Endpoint Analyses

No imputations will be made for missing secondary endpoint data.

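### SAP 5.6.7: a ceiling of 150 treated does not follow from 125 and 20% dropout (that takes 157), and 20%/150 conflicts with the protocol's 15%/147

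*SAP*

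**What the plan says.** SAP 5.6.7 (Table 4) gives 125 as the number needed for 90% power on the MBL co-primary endpoint, with an assumed success rate of 60% and a lower confidence limit of at least 45%. It gives 75 for surgical reintervention (90% assumed, limit 75%). On method it says: "The co-primary endpoint of Reduction in MBL at 12 months will be analyzed using 95% exact confidence intervals". It then makes the dropout allowance, as a number treated: "To account for an assumed 20% subject dropout rate (subjects lost to follow-up), a sample size of at least 125 and up to 150".

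Protocol section 8 starts from the same base number: "The sample size for this study is at least 125 treated subjects to achieve 90% power". Its allowance differs: "To allow for 15% loss to follow-up, up to 147 women will be enrolled and treated". It then points elsewhere for the reasoning: "The statistical rationale for this sample size may be found in the Statistical Analysis Plan".

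Protocol 19.1 gives 125 as the number for power (part A) and adds in part C: "To account for an assumed 15% subject dropout rate (subjects lost to follow-up at the 12-month visit), a sample size of 147 treated subjects". Protocol section 4G (Number of Subjects) also gives a flat figure: "147 treated subjects; at least 50% will be enrolled and treated within the United States".

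**The concern.** There are three faults.

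- **The SAP's step from 125 to 150 does not close.** If 20% of 150 are lost, 120 remain.
- **The two documents disagree on the dropout rate (20% against 15%) and on the maximum (150 against 147).** The protocol names the SAP as the source of the rationale, so a reader who follows that reference finds different inputs. SAP 5.7 reports no changes to planned analyses and does not explain the difference.
- **The 125 is worded as a treated minimum in both documents**, although the power calculation needs 125 women for analysis. Read literally, enrolment could stop at 125 treated with no allowance for loss. Protocol section 8 also treats 147 as a ceiling, while 4G and 19.1C treat it as the number.

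At stake is whether the sample-size statement of a pivotal single-arm study can be traced: which dropout rate was planned for, and whether 125 counts women treated or women analysed.

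**Working it through.** **Inputs.** MBL threshold 0.45, assumed rate 0.60, N = 125, exact two-sided 95% interval (SAP 5.6.7, protocol 19.1A). Reintervention-free threshold 0.75, assumed rate 0.90, N = 75 (SAP Table 4, protocol 19.1B). Dropout 20% with 125 to 150 treated (SAP 5.6.7); 15% with 147 treated (protocol 8 and 19.1C).

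**Step 1: the base numbers reproduce.** Success needs the Clopper-Pearson lower limit, the 0.025 quantile of Beta(x, n − x + 1), to reach the threshold. Power is P(X ≥ x_min) for X binomial with n and the assumed rate.

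- MBL, n = 125: x_min = 68, power 91.4%. It is the smallest n from which power stays at or above 90%.
- Reintervention, n = 75: x_min = 64, power 93.1%. It too is the smallest n from which power stays at or above 90%. This is a simple binomial approximation to the planned life-table analysis.

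The error is therefore confined to the dropout step.

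**Step 2: the SAP's dropout step.** To keep n after a proportion d is lost, treat n/(1 − d).

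- 125/(1 − 0.20) = 156.25, so 157 treated.
- 150 × 0.80 = 120 remaining.
- Loss that 150 can absorb: 1 − 125/150 = 16.7%.
- Shortfall: 157 − 150 = 7, and 7/157 = 4.5%.
- 125 × 1.20 = 150. The SAP prints no formula, but its figure matches this shortcut.

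**Step 3: the protocol's dropout step.** 125/0.85 = 147.06, and 147 × 0.85 = 124.95. Strict rounding up gives 148, a trivial difference. The protocol's pair is coherent. At the SAP's 20%, 147 would leave 147 × 0.80 = 117.6, about 118.

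**Step 4: exact MBL power at the resulting numbers** (true rate 0.60).

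| n analysed | How it arises | x_min | Power |
|---|---|---|---|
| 100 | 125 treated less 20% | 56 | 82.1% |
| 118 | 147 less 20% | 65 | 88.1% |
| 119 | neighbour | 65 | 90.1% |
| 120 | 150 less 20% | 66 | 88.7% |
| 121 | neighbour | 66 | 90.6% |
| 124 | 147 less 15%, rounded down | 68 | 89.6% |
| 125 | base number | 68 | 91.4% |
| 147 | all treated analysed | 79 | 94.8% |
| 150 | all treated analysed | 80 | 95.9% |
| 157 | all treated analysed | 84 | 95.9% |

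Reintervention at n = 120: x_min = 100, power 99.2%, so that endpoint is not threatened.

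**The case against.** The strongest reply is that the primary analysis does not work on women with complete 12-month data. SAP 5.6.8.2 carries the last observation forward for missing MBL data and censors dropouts in the life-table analysis, and the full analysis set keeps all treated women apart from two exclusions. Most women lost after an earlier PBAC would therefore still count. If every treated woman were analysed and 60% held after imputation, 150 and 157 would give the same 95.9%. The dip at 120 is also partly the saw-tooth of the exact test, since 119 gives 90.1%. This limits the consequence, and it stands. It does not repair the derivation: the SAP itself chose to inflate 125 for loss to follow-up, and on those terms 150 is not the answer. Carry-forward also needs an earlier PBAC, and women who have a reintervention for fibroid symptoms before 12 months are left out of the MBL analysis.

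A second reply is that 147 lies inside the SAP's 125 to 150, and that protocol 19.1 shows in order how 125 becomes 147, so the operative plan is clear. Both points are fair. The conflict is in the rate and the maximum, and not in every permitted N. It still needs resolving, because the protocol sends the reader to the SAP.

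A third is that the SAP differs from the protocol elsewhere too (device name, maximum number of fibroids, uterine volume limit, 3-month PBAC), so this may be one sign of a SAP that was not brought into line with the protocol. The visible text does not settle that. It would argue for a wider reconciliation, not for leaving this sentence as it is.

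**Conclusion.** The concern holds. On the SAP's own inputs the maximum should be 157, not 150: 7 women, or 4.5%, short. The SAP's 20% and 150 conflict with the protocol's 15% and 147, and the 125 floor, as worded, carries no dropout allowance.

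The practical effect is small. Complete-case MBL power at 120 is 88.7%, 1.3 points under the 90% target. At the protocol's 147 less 15% it is 89.6% to 91.4%, depending on whether 124 or 125 remain. If all treated women were analysed, it would be 94.8% at 147 and 95.9% at 150, before any exclusions from the full analysis set or for reintervention. These figures assume a true success rate of 60%, and that the rate is unchanged by imputation where carried-forward values are counted.

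The text should be corrected. Nothing here shows that the trial is underpowered at 147.

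**What to change.** **Preferred: adopt the protocol's figures in SAP 5.6.7.** Suggested text:

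> Allowing for 15% of subjects being lost by the 12-month visit, 147 subjects will be enrolled and treated, so that about 125 are expected to have 12-month data. The 125 in Table 4 is the number evaluable, not a minimum number treated. Complete-case exact power for MBL at 125 is 91.4%. The number in the primary MBL analysis may differ, because missing values are carried forward and women with a prior reintervention are excluded.

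In protocol section 8, describe 125 as the evaluable number and give 147 in the same form as 4G and 19.1C.

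**If 20% is kept:** state that 125 evaluable takes 157 treated, or keep 150 and state that it leaves 120 with complete-case power of about 89%. Align protocol 4G, 8 and 19.1C either way.

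**Cost.** The preferred route is wording in two places, plus whatever IRB/EC submission or notification protocol 16.2 requires, and no extra patients. Keeping 20% costs either 7 more treated women than 150 or a stated complete-case power just under 90%.
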